**A6.2 Exclusion Criteria for Selection of Historical Control Group**

All responses must be “no” to include a record in the study:

1. A known history of continued CDI diarrhea despite being on a course of antibiotics prescribed for CDI treatment.
2. Required continuous antibiotic therapy for a condition other than CDI.
3. Previous successful (resolution of CDI diarrhea) fecal transplant for recurrent CDI < 6 months prior to the date the most recent sequence of multi-recurrent CDI began.
4. Previous unsuccessful (recurrent CDI diarrhea was unresolved) fecal transplant.
5. Previous treatment with RBX2660.
6. Diagnosis of inflammatory bowel disease (IBD), e.g., ulcerative colitis, Crohn’s disease, or microscopic colitis.
7. Diagnosis of irritable bowel syndrome (IBS) as determined by Rome III criteria.
8. History of chronic diarrhea due to causes other than *C. difficile*.
9. History of celiac disease.
10. Disease symptoms caused by a confirmed intestinal pathogen other than *C. difficile*.
11. Colostomy.
12. Intraabdominal surgery within 60 days prior to the date the most recent sequence of multi-recurrent CDI began.

[REDACTED]

[REDACTED]

[REDACTED]

[REDACTED]

[REDACTED]

[REDACTED]

[REDACTED]

[REDACTED]

[REDACTED]

[REDACTED]

[REDACTED]

18. Life expectancy of < 12 months at initiation of treatment for CDI.

19. Compromised immune system [REDACTED]

[REDACTED]

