#### 4.2 Exclusion Criteria

All responses must be “no” to include a subject in the study:

1. A known history of continued CDI diarrhea despite being on a course of antibiotics prescribed for CDI treatment.
2. Requires continuous antibiotic therapy for a condition other than CDI.
3. Previous successful (resolution of CDI diarrhea) fecal transplant for recurrent CDI < 6 months prior to study enrollment.
4. Previous unsuccessful (recurrent CDI diarrhea was unresolved) fecal transplant.
5. Previous treatment with RBX2660.
6. Diagnosis of inflammatory bowel disease (IBD), e.g., ulcerative colitis, Crohn’s disease, or microscopic colitis.
7. Diagnosis of irritable bowel syndrome (IBS) as determined by Rome III criteria.
8. History of chronic diarrhea.
9. History of celiac disease.
10. Disease symptoms caused by a confirmed intestinal pathogen other than *C. difficile*.
11. Colostomy.
12. Intraabdominal surgery within the last 60 days.

[REDACTED]

[REDACTED]

[REDACTED]

[REDACTED]

[REDACTED]

[REDACTED]

[REDACTED]

[REDACTED]

18. Life expectancy of < 12 months.
19. Compromised immune system [REDACTED]
- [REDACTED]
- [REDACTED]
- [REDACTED]
- [REDACTED]
- [REDACTED]
- [REDACTED]
- [REDACTED]
- [REDACTED]
- [REDACTED]

[REDACTED]

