### 8.3 Analysis of Efficacy

The primary endpoint is: Efficacy, measured by the recurrence-free rate of CDI diarrhea without the need for retreatment with *C. difficile* anti-infective therapy or fecal transplant through 56 days after completion of study treatment with RBX2660. The primary analysis will compare the proportion of subjects in the treatment arm who are recurrence-free to the proportion of historical controls who are recurrence-free. [REDACTED]

[REDACTED] An efficacy and safety data-received-to-date analysis will be conducted on the treatment group subjects when approximately 100 of them

complete their 8-week assessment. [REDACTED]

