**A2. Objective**

The objective of the antibiotic-treated historical control is to obtain a closely matched data set of the standard of care antibiotic treatment for recurrent CDI comparison to provide an adequate and well-matched set of data for the efficacy analysis of RBX2660.

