#### **A4. Study Design and Methods**

This is a retrospective chart review of patients treated with antibiotics for recurrent CDI who match key inclusion/exclusion criteria from the clinical study (see below). Patients will not be contacted. A waiver of Informed Consent/HIPAA authorization for the collection of chart data will be obtained from each site's IRB prior to beginning the chart review process. Site personnel will review their patient databases and identify patients with a diagnosis of multi-recurrent CDI, which is defined as a documented diagnosis of the return of CDI diarrhea ( $\geq 3$  watery stools in  $\leq 24$  hours for at least two consecutive days) that begins less than 8 weeks after completion of a CDI treatment regimen that resulted in the cessation of CDI symptoms. The diagnosis must include at least one positive *C. difficile* test on record. The identified charts will be accessed by the designated qualified and trained chart reviewer at the site. All patient records

on the list will be reviewed and a log will be kept documenting the review and why a record was excluded from the final historical control data set.

Data collection includes:

- demographics (age at the time of the start of data collection, gender, race, ethnicity);
- pre-existing conditions;
- concomitant medications;
- CDI history including each episode's start/stop dates, signs/symptoms, treatment(s) received, outcomes, and CDI-related hospitalizations;
- Blood and stool test results;
- Vital signs;
- Adverse events as recorded in the chart. (see Section 7.0 of the study protocol for all definitions). Adverse events will be adjudicated for seriousness, severity, and causality by the site investigator at the time of data collection as best as possible given the description of the event in the medical record.

[REDACTED]

All data and records will be kept in strict confidentiality as required by law and as stated in Section 9.4 of the study protocol.

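### Exclusion item 8 is broader for RBX2660 subjects than for historical controls, so on a literal reading some patients with antibiotic-responsive, long-relapsing CDI could enter only as controls

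*Protocol*

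**What the plan says.** Protocol 4.2 lists the exclusions for RBX2660 subjects under the rule "All responses must be “no” to include a subject in the study". Item 8 there is "History of chronic diarrhea", with nothing further. Appendix 1, A6.2, lists the exclusions for control records under the matching rule "All responses must be “no” to include a record in the study". Its item 8 is "History of chronic diarrhea due to causes other than *C. difficile". Neither item is redacted, and no visible text defines chronic diarrhea or says whether repeated CDI episodes count as such.

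Item 1 is the same in both lists: "A known history of continued CDI diarrhea despite being on a course of antibiotics prescribed for CDI treatment". A4 also requires that a control's recurrence be one "that begins less than 8 weeks after completion of a CDI treatment regimen that resulted in the cessation of CDI symptoms".

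A2 states that the control set is meant "to provide an adequate and well-matched set of data for the efficacy analysis of RBX2660". Protocol 8.3 gives the use made of it: "The primary analysis will compare the proportion of subjects in the treatment arm who are recurrence-free to the proportion of historical controls who are recurrence-free". SAP 4.4 confirms that nobody is randomised.

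**The concern.** With no randomisation, common eligibility is the main visible means of making the two groups comparable. A criterion that admits a type of patient to one group only undermines this. Here the criterion concerns earlier diarrhea and the endpoint is itself the absence of CDI diarrhea, so the mismatch bears directly on the outcome.

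The difference does not look like an adaptation to chart review. A retrospective list needs changes of tense and reference date, but it does not need a cause added to a diagnosis.

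If long-relapsing patients do worse and enter only as controls, the control recurrence-free rate falls and RBX2660 looks better than it is. The mismatch can also reach the Per Protocol Population, since SAP 6.3 removes eligibility violations: the same history could be a violation in one group and not in the other. Finally, sites that read 4.2 item 8 differently would enrol different patients.

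**Working it through.** **Step 1. Compare the two lists item by item (Protocol 4.2 against A6.2).**

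| Items | Comparison |
|---|---|
| 1, 4-7, 9-11 | Same wording |
| 2, 3, 12, 18 | Differ only in tense or reference date |
| 8 | Scope differs: any cause (4.2), non-CDI causes only (A6.2) |
| 13-17, rest of 19 and after | Redacted, cannot be compared |

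Item 8 is the only fully visible exclusion whose clinical scope changes.

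**Step 2. Find who is affected.**

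- CDI diarrhea that continued on antibiotics: out of both groups under item 1. For controls, the A4 definition also requires that earlier treatment stopped the symptoms.
- Chronic diarrhea from another cause: out of both groups under item 8.
- CDI diarrhea that responded to antibiotics, relapsed over a long period, and is recorded as chronic diarrhea: out of RBX2660 if 4.2 item 8 is read literally, and allowed as a control.

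Only the third group is treated differently.

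**Step 3. Possible size.** The documents state no figure to reproduce: the assumed rates, alpha and power are not visible. The inputs are therefore:

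- Control recurrence-free rate of 35%, a benchmark taken as 100% minus the 65% recurrence after two relapses quoted in A3.
- Share f of controls in the third group: 10-20% (assumed).
- Their recurrence-free rate r: 15-25% (assumed).

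Control rate = (1 - f) × 35% + f × r. Shift = f × (35% - r).

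| f | r | Control rate | Shift (points) |
|---|---|---|---|
| 10% | 25% | 31.5 + 2.5 = 34.0% | 1.0 |
| 10% | 15% | 31.5 + 1.5 = 33.0% | 2.0 |
| 20% | 25% | 28.0 + 5.0 = 33.0% | 2.0 |
| 20% | 15% | 28.0 + 3.0 = 31.0% | 4.0 |
| 0%, or r = 35% | | 35.0% | 0 |

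**Step 4. What such a shift does to a test.** Illustration only, assuming a pooled two-proportion normal test at two-sided 5%, and no true effect (35% in the RBX2660 arm). With d the shift, the chance of wrongly declaring RBX2660 superior is 1 - Φ((1.96 × SE0 - d) / SE1). SE0 is the pooled and SE1 the unpooled standard error.

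For d = 4 points with 150 against 100 (the SAP 4.5 sizes), the pooled rate is (150 × 0.35 + 100 × 0.31) / 250 = 0.334, SE0 = 0.0609 and SE1 = 0.0605. This gives z = 1.31 and a probability of 9.5%. For d = 1 point it is 3.6%. The nominal value is 2.5%. With 200 controls (the upper figure in A7), the two values are 12.2% and 3.9%.

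**The case against.** The strongest reply is that 4.2 item 8 was never meant to cover CDI diarrhea. Inclusion item 2 requires repeated CDI, and items 6 to 10 list competing causes of diarrhea: IBD, IBS, celiac disease, another pathogen. In that company item 8 most naturally means non-CDI diarrhea, and A6.2 only spells this out for chart reviewers. If all sites read it so, the groups match on this item and there is no bias. Nothing visible shows that the literal reading was applied. This stands, and it is why the bias is conditional. It does not remove the ambiguity, since 4.2 alone does not tell a site which reading to use.

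Direction and size are also open. A3 ties recurrence risk to the number of relapses, not to duration or to a chart label of chronic diarrhea. A worse prognosis is plausible but not shown. The 35% benchmark may already include such patients. If 35% is the blended rate, the remaining controls are at (35 - f × r) / (1 - f), which is 36.1% for f = 10%, r = 25% and 40.0% for f = 20%, r = 15%. The gap is then 1.1 to 5.0 points, so the order of magnitude holds.

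SAP 5.1 says that controls were matched on several baseline factors, and parts of the method text are redacted. The hidden text may deal with this, so its absence is not held against the plan.

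A reader might infer that longstanding C. difficile diarrhea in general can enter only the control group, or that the comparison is known to be biased towards RBX2660. The documents support neither: item 1 and the A4 definition remove antibiotic-unresponsive disease, and the bias depends on a reading and on a prognosis that the documents do not establish.

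**Conclusion.** The mismatch in wording is certain, and it matters enough to correct because the primary result rests on a non-randomised comparison with a control set described as well matched. Its effect is uncertain. It is confined to patients with antibiotic-responsive, long-relapsing CDI whose charts record chronic diarrhea, and it arises only if 4.2 item 8 is read literally. Under the assumed shares and rates the control recurrence-free rate would be about 1 to 4 points too low, in favour of RBX2660. It would be unaffected under the contextual reading or with equal prognosis. Confidence is high on the text and moderate at most on the consequence.

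**What to change.** 1. Reconcile Protocol 4.2 item 8 and A6.2 item 8 so that one identically worded criterion applies to both groups, with chronic diarrhea defined. Which scope is intended is for the sponsor to settle.
2. Rewording does not change who has already been screened out, and SAP 5.1 speaks of the controls as already chosen. So also prespecify, before the comparison is run, a sensitivity analysis that repeats the primary comparison without control records that would fail the literal 4.2 wording. These can be identified from the pre-existing conditions and CDI episode dates abstracted under A4. The main and sensitivity results then show the comparison under each reading of item 8.
3. Report how many control records are removed. If the screening log kept under Protocol 9.12 records reasons, also report how many candidates were refused RBX2660 under item 8. That would show whether the literal reading was used.

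The cost is a short protocol change and one further analysis, with somewhat fewer controls and therefore less precision in that analysis. A4 does not list the cause of chronic diarrhea as a data item, so attribution to C. difficile may have to be inferred from the chart data. The rule for doing so should be written down in advance.

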**A7. Statistical Considerations**

Approximately up to 200 subjects (minimum of 100) will be included in the historical control group to appropriately power the primary efficacy study endpoint (see Section 8.0 Statistical Considerations in the study protocol and the Statistical Analysis Plan).

1 LIST OF ABBREVIATIONS AND DEFINITIONS OF TERMS

Abbreviation	Definition
AE	adverse event(s)
ATC	anatomical therapeutic chemical
BLA	Biologics License Application
BMI	Body Mass Index (kg/m ²)
CI	confidence interval
CDI	Clostridium difficile infection
CSR	Clinical Study Report
eCRF	electronic case report form
FT	fecal transplant
HLGT	high level group term
HLT	high level term
IBS	irritable bowel syndrome
ICU	intensive care unit
IQR	interquartile range
LLT	lower level term
MedDRA	Medical Dictionary for Regulatory Activities
mL	milliliters
N	number of subjects
PT	preferred term
RBX2660	investigational drug product being evaluated
SAE	serious adverse event
SAP	Statistical Analysis Plan
SD	standard deviation
SF-36	36-item short form health survey instrument
SOC	system organ class
SOP	Standard Operating Procedure
TEAE	treatment-emergent adverse event
WHO	World Health Organization

2 INTRODUCTION

RBX2660 (microbiota suspension) is being studied for the treatment of adult subjects as an adjunct to antibiotics for the treatment of recurrent *Clostridium difficile* infection (CDI). The purpose of this study is to evaluate the efficacy and safety of RBX2660 for the treatment of recurrent CDI in subjects who have had either a) at least two recurrences after a primary episode (i.e., at least three episodes) and have completed at least two rounds of standard-of-care oral antibiotic therapy or b) have had at least two episodes of severe CDI resulting in hospitalization.

3 STUDY OBJECTIVES AND ENDPOINTS

3.1 Primary Objective

The primary objective of this study is to compare the efficacy, defined as the absence of CDI diarrhea without the need for retreatment with *C. difficile* anti-infective therapy or fecal transplant (FT) through 56 days after treatment, of one treatment with RBX2660 (one treatment consists of two enemas of RBX2660 7 ± 2 days apart) versus antibiotic-treated historical controls.

3.2 Secondary Objectives

The secondary objectives of this study are:

1. To evaluate the safety of RBX2660.
2. To evaluate the effect of RBX2660 on pre-existing conditions other than recurrent CDI.
3. To evaluate quality of life as measured by the SF-36 Health Survey.
4. To evaluate the efficacy of *C. difficile* anti-infection therapies administered to confirmed treatment failures.

3.3 Primary Endpoint

Efficacy, measured by the recurrence-free rate of CDI diarrhea without the need for retreatment with *C. difficile* anti-infective therapy or fecal transplant through 56 days after completion of

study treatment with RBX2660, will be evaluated by comparing the recurrence-free rate observed in the study population to the recurrence-free rate identified from antibiotic-treated historical controls.

3.4 Secondary Endpoints

The secondary endpoints for this study are:

1. The frequencies and severity grades of solicited AEs from the first day of assigned study treatment through seven days following the last enema of assigned study treatment will be collected.
2. Adverse events, including serious adverse events and the onset of new chronic diseases, will be collected at in-office visits at 1, 4, and 8 weeks and at 3-, 6-, and 12-month calls; they will be categorized by frequency, severity, seriousness, and causality.
3. Serious adverse events and new onset of chronic diseases will be collected at a telephone call at 24 months and will be categorized by frequency, severity, seriousness, and causality.
4. Frequencies of major complications of CDI including death, septic shock, toxic megacolon, colonic perforation, emergency colectomy, or ICU admission will be collected through the 24-month telephone assessment.
5. The effect of RBX2660 on pre-existing conditions other than recurrent CDI will be assessed by comparing the change in the condition throughout the course of the study.
6. SF-36 scores recorded at the Week 8 visit will be compared to scores recorded at the screening visit.
7. Efficacy of *C. difficile* anti-infection therapies administered to confirmed treatment failures will be compared to each other for the rates of success at resolving CDI diarrhea for at least 56 days after completion of the anti-infection therapy.

4 STUDY DESIGN

4.1 General Design

This is a prospective, multicenter, open-label study assessing the efficacy and safety of RBX2660 as an adjunct to antibiotics for the treatment of recurrent CDI. Up to approximately 150 subjects will be enrolled in this study and receive RBX2260. Approximately 100 historical controls will be chosen from a retrospective chart review of patients treated with antibiotics for recurrent CDI who match key inclusion/exclusion criteria from the study.

Subjects who meet all inclusion and exclusion criteria, including having a positive *C. difficile* test within 60 days prior to enrollment and experiencing either a) at least two recurrences after a primary episode (diagnosis must include at least one positive *C. difficile* test on record within 60 days prior to enrollment) and have completed at least two rounds of standard-of-care oral antibiotic therapy or b) have had at least two episodes of severe CDI resulting in hospitalization prior to enrollment, will receive open-label treatment with RBX2660. One study treatment consists of two RBX2660 enemas administered 7 ± 2 days apart; the second enema may be administered sooner if CDI diarrhea reoccurs in less than 7 days. Subjects will already be taking or will start a course of antibiotics to control recurrent CDI diarrhea at the time of enrollment, [REDACTED]

[REDACTED] An in-office follow-up visit will occur at 8 weeks after completing study treatment for the assessment of AEs, efficacy, collection of the Subject Diary, and blood tests. Telephone assessments for AEs including serious adverse events (SAEs) and the new onset of chronic diseases and CDI symptoms will occur at weeks 1, 2, 3, and 4 and at 3, 6, and 12 months after completing study treatment. Assessment of serious adverse events and the new onset of chronic diseases will occur via phone call at 24 months after completing study treatment. Subjects will keep a detailed Subject Diary to assess for solicited adverse events from the date of enrollment to one week after completing study treatment (second enema). Treatment

failures (as determined by the site investigator at the time of CDI recurrence) are eligible to receive another therapy deemed most appropriate by their study investigator.

[REDACTED]

4.1.2 Definition of CDI Diarrhea

Clostridium difficile diarrhea is defined as the passage of ≥ 3 watery stools in 24 or fewer consecutive hours for at least two consecutive days.

4.1.3 Definition of Treatment Success

Treatment success is defined as the absence of CDI diarrhea without the need for retreatment with *C. difficile* anti-infective therapy or FT through 56 days after completion of study treatment.

4.1.4 Definition of Treatment Failure (CDI Recurrence)

Treatment failure (CDI recurrence) is defined as: 1) the presence of CDI diarrhea (see Section 4.1.2), with or without other CDI symptoms, < 56 days after administration of the last assigned study enema; 2) a positive stool test for *C. difficile*; 3) need for retreatment for *C. difficile* infection; and 4) no other cause for CDI symptoms has been determined. [REDACTED]

[REDACTED]

[REDACTED]
[REDACTED]

4.1.5 Management of Treatment Failures

Treatment failures (as determined by the site investigator at the time of CDI recurrence) are to be treated with another therapy(ies) deemed most appropriate by their study investigator.

4.1.6 Determination of Treatment Success/Failure

The site investigator makes the determination of success based on the absence of CDI diarrhea without the need for retreatment with *C. difficile* anti-infective therapy or FT at less than 56 days after administration of the last assigned study enema; [REDACTED]

[REDACTED]
[REDACTED]
[REDACTED]
[REDACTED]
[REDACTED]

4.2 Discussion of Study Design

Screening will be performed before treatment and will include demographics, a complete medical history, a review of inclusion/exclusion criteria, stool and blood testing, a modified physical exam, Form SF-36 completion, vital signs, Subject Diary recording, and urine pregnancy test for all females of childbearing potential.

The target population is adults (≥ 18 years old) with recurrent CDI who have had either a) at least two recurrences after a primary episode [REDACTED] and have completed at least two rounds of standard-of-care oral antibiotic therapy or b) have had at least two episodes of severe CDI resulting in hospitalization.

For study entry, recurrent CDI is defined as a documented diagnosis of recurrent CDI (recurrence of CDI symptoms for at least two consecutive days that begins less than 8 weeks after completion of CDI treatment) and at least one positive stool test for the presence of *C. difficile* on record within 60 days prior to enrollment.

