## 4.0 Treatment Subject Selection and Withdrawal

### 4.1 Inclusion Criteria

All responses must be “yes” to include a subject in the study:

1.  $\geq 18$  years old.
2. Medical record documentation of recurrent CDI including a positive *C. difficile* test within 60 days prior to enrollment and either: a) at least two recurrences after a primary episode and has completed at least two rounds of standard-of-care oral antibiotic therapy or b) has had at least two episodes of severe CDI resulting in hospitalization.
3. Already taking or will start a course of antibiotics to control recurrent CDI symptoms at the time of enrollment. [REDACTED]

4. Willing and able to have an enema(s).
5. Willing and able to complete the stool and serum testing required for the study.

6. [REDACTED]
- [REDACTED]
- [REDACTED]
- [REDACTED]
- [REDACTED]
- [REDACTED]
- [REDACTED]
- [REDACTED]
- [REDACTED]
- [REDACTED]

10. [REDACTED]
11. Willing to complete the required Subject Diary.
12. Willing and able to meet all study requirements, including completing the assessment visit and phone calls.

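### SAP 4.2 and Protocol Appendix 1 (A4, A6.1) define the qualifying recurrence differently for RBX2660 subjects and historical controls; align them and test sensitivity in both arms

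*SAP*

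**What the plan says.** **RBX2660 subjects.** SAP 4.2 (Discussion of Study Design) opens its definition with "For study entry, recurrent CDI is defined as a documented diagnosis of recurrent CDI". It then explains this as "recurrence of CDI symptoms for at least two consecutive days that begins less than 8 weeks after completion of CDI treatment", and adds a positive stool test "on record within 60 days prior to enrollment". Protocol 4.1, inclusion 2, also asks for a positive "test within 60 days prior to enrollment and either: a) at least two recurrences after a primary episode" or, alternatively, two severe hospitalized episodes.

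**Historical controls.** Protocol Appendix 1, A4 looks for a "documented diagnosis of the return of CDI diarrhea", gives the stool-count threshold, and requires a return "that begins less than 8 weeks after completion of a CDI treatment regimen that resulted in the cessation of CDI symptoms". A4 asks for at least one positive test on record. A6.1, inclusion 2, places that test at the original diagnosis.

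**Purpose.** A2 states the aim as "to obtain a closely matched data set of the standard of care antibiotic treatment", and SAP 5.1 repeats it.

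Protocol 3.3, Definition of Recurrent CDI for Study Entry, appears in the table of contents, but its text is blacked out.

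**The concern.** A historical-control comparison has no randomization to balance the arms, so it depends on both arms being selected by the same disease definition. Two mismatches are visible here.

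- **Clinical threshold.** On the SAP wording, an RBX2660 subject could qualify on a return of symptoms short of CDI diarrhea, or after treatment that had not cleared the earlier episode. The A4 wording would not admit such a control. Subjects without a true diarrheal recurrence may be more likely to stay free of CDI diarrhea for 56 days whatever they receive, which would favor RBX2660.
- **Laboratory confirmation.** A control can qualify on recurrences that were never tested. If some were not CDI, control success would rise, which would work against RBX2660.

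Each could move the difference in recurrence-free rates for reasons unrelated to the product.

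**Working it through.** The unredacted text states no figure to reproduce; the sample-size assumptions are blacked out. The check is a comparison of wording, followed by an illustration of scale.

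**1. Side by side**

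| Element | RBX2660 (SAP 4.2, Protocol 4.1/4.2) | Controls (A4, A6.1, A6.2) | Looser for |
|---|---|---|---|
| Clinical sign | CDI symptoms, two consecutive days | CDI diarrhea, ≥3 watery stools in ≤24 h, two consecutive days | RBX2660 |
| Earlier regimen stopped symptoms | Not stated | Required | RBX2660 |
| Interval after treatment | Less than 8 weeks | Less than 8 weeks | Same |
| Documented diagnosis | Required | Required | Same |
| Positive test | Within 60 days before enrollment | At original diagnosis, no recency window | Controls |
| Number of recurrences, or severe hospitalized episodes | Criteria (a) or (b) | Same criteria | Same |
| Exclusion 1 (known continued diarrhea on CDI antibiotics) | Present | Same wording | Same |

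**2. Is the symptoms wording really broader?** The failure definition (Protocol 3.6, SAP 4.1.4) counts CDI diarrhea with or without other CDI symptoms, so diarrhea is one symptom among several. SAP 4.1.2 defines CDI diarrhea, and SAP 4.1.3 and 4.1.4 use that term for the outcome. SAP 4.2 does not use it for entry. Read literally, a subject can enter on a wider condition than the one that counts as failure.

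**3. Scale of the clinical-threshold difference alone.** Assume no product effect and a base recurrence-free rate of 100% − 65% = 35%, using the recurrence rate after two relapses in A3. Let f be the share of RBX2660 subjects entering on symptoms alone and s their recurrence-free rate. The documents give neither f nor s.

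Spurious difference = f × (s − 0.35)

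| f | s = 0.55 | s = 0.80 | s = 0.95 |
|---|---|---|---|
| 5% | 1.0 points | 2.25 points | 3.0 points |
| 10% | 2.0 points | 4.5 points | 6.0 points |
| 20% | 4.0 points | 9.0 points | 12.0 points |

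**4. Chance of a nominally significant result favoring RBX2660.** Assume a two-sided 5% pooled z-test with 150 RBX2660 subjects and 100 controls (SAP 4.5), so that the nominal chance in that direction is 2.5%. With d the difference, the chance is Φ[(d − 1.96 × SE₀)/SE₁], where SE₀ is the pooled and SE₁ the unpooled standard error.

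Example, f = 10% and s = 0.95:
- RBX2660 rate 0.41, control rate 0.35, d = 0.06.
- Pooled rate (150 × 0.41 + 100 × 0.35)/250 = 0.386.
- SE₀ = √[0.386 × 0.614 × (1/150 + 1/100)] = 0.0629.
- SE₁ = √[0.41 × 0.59/150 + 0.35 × 0.65/100] = 0.0624.
- Φ(−1.01) = 15.5%.

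Over s = 0.55 to 0.95 the chance is 3.6–6.9% at f = 5%, 5.0–15.5% at f = 10% and 9.2–46.8% at f = 20%. With 200 controls (the upper figure in A7), f = 20% gives 11.7–62.0%.

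**5. Both differences together.** Let g be the share of controls admitted on recurrences that were not CDI, and t their recurrence-free rate.

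Net spurious difference = f(s − 0.35) − g(t − 0.35)

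With s = t = 0.95:
- f = 10%, g = 0: +6 points.
- f = 10%, g = 10%: 0 points.
- f = 5%, g = 20%: 3 − 12 = −9 points.

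The sign depends on quantities that the documents do not give.

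**The case against.** A reader might infer that milder or uncertain recurrences can enter only the RBX2660 arm, so that its success rate is inflated. The documents do not support that, for four reasons.

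- **The operative definition is not visible.** SAP 4.2 is a discussion section, and enrollment follows the protocol. Protocol 3.3 is blacked out and could match A4 exactly. The SAP text just before 4.1.2 is blacked out as well.
- **Uncertain recurrences can also enter the control arm.** The test requirement for controls is the looser one.
- **The SAP wording carries other conditions.** It also requires a documented diagnosis and a recent positive test, and the numbered recurrence criteria match across arms. Exclusion 1 is shared, which narrows the gap on prior response.
- **It may be loose drafting.** Antibiotics at enrollment control CDI diarrhea in Protocol 3.2 and CDI symptoms in Protocol 4.1.

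These points remove the one-way claim but leave the mismatch. If Protocol 3.3 matches SAP 4.2, the arms use different definitions. If it matches A4, SAP 4.2 misstates the entry rule. Exclusion 1 removes known persistent diarrhea on antibiotics, which is less than requiring that symptoms had ceased. The 60-day test is not tied to the qualifying recurrence in the visible text, so a test from the previous episode could satisfy it.

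The Per Protocol population (SAP 6.3) already drops violations of the protocol's recurrence definition, and SAP 8.7.1 repeats the efficacy analysis on it. That helps only in part, because the yardstick is the protocol definition and nothing visible shows that it is common to both arms.

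**Conclusion.** The point holds as a mismatch of definitions. SAP 4.2 is looser than A4 on the clinical threshold and on prior response, while A6.1 is looser than SAP 4.2 and Protocol 4.1 on laboratory confirmation. That is hard to square with a closely matched control set. Whether anyone enrolled under a looser rule is not shown, and the net direction of bias is unknown.

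The 2 to 12 points (f = 5–20%, s = 80–95%) illustrate one of the two differences. They rest on an assumed f and s, a 35% base rate taken from background literature, and no misclassified controls. They are not an estimate of inflation in this trial. The issue merits correction because even modest shares could matter in an unrandomized, open-label comparison.

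**What to change.** 1. **One definition.** Reconcile SAP 4.2, Protocol 3.3, A4 and A6.1 so that a single recurrence definition applies to both arms. It should state the clinical threshold, whether the earlier regimen must have stopped symptoms, and the timing of the positive test relative to enrollment or to the index date used for controls.
2. **Sensitivity analysis in both arms.** Repeat the primary analysis with RBX2660 subjects and controls both restricted to records that meet the common definition. Report how many in each arm fail each element, and how many cannot be classified. Screening only the RBX2660 arm would leave the test-timing difference untouched.

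**Cost.** Wording changes and one further analysis. Protocol 3.7 has CDI episodes captured in detail, and A4 collects dates, signs and symptoms, treatments, outcomes and stool results for controls, so much of the input should exist. Whether stool counts and symptom cessation were recorded is not visible, and some records may lack the detail. The analysis will include somewhat fewer subjects. Rewording the definition does not change who has already been enrolled or selected, so the analysis is what informs interpretation.
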